Outcome data will be examined for homogeneity of variance, and if necessary transformed to meet this criterion. As this is a within-subjects design, repeated measures analysis of covariance (ANCOVA) will be used to analyze the primary outcome, with drug condition as the within-subjects factor. Similarly, for secondary outcome measures, repeated measured ANCOVA will also be used. A probability level of 0.05 or lower will be considered significant.

As for the neuroimaging data, we will use AFNI software to analyze our data. As a first step we will preprocess the data to correct for motion and then realign the functional volumes to the anatomical volumes. Subsequently, we will perform a regression analyses. Voxels are considered active if the total variance accounted for by the best-fit combination of the regressors of interest will exceed a chosen F ratio ($P = 0.05$ per voxel, uncorrected for multiple comparisons). We will also perform a subtraction analyses between different BOLD responses. To create the average activation maps, we will perform a random effect approach (activation amplitude and t -values will be averaged in each voxel in standardized space across subjects). Group maps will thresholded using 3dClustSim (an analysis module within AFNI). A cluster size of at least 5 voxels will be determined by Monte Carlo simulation.

2. Power analysis

We chose an effect size $d_z = 0.4$ which is consistent with effect sizes of cue reactivity observed for other medications like naltrexone, acamprosate and topiramate. Considering the following parameters: $d_z = 0.4$, α err prob = .05, and power ($1 - \beta$ err prob) = .80, a sample size of 41 subjects will be needed. For fMRI, our sample size of $n=27$ is based on the study by Hariri and colleagues (Hariri et al. 2002) , who used the same task in an fMRI study (between subjects design) with a similar sample size subjects.

3. Accrual number

Consistent with the within-subject design, our previous protocol testing the same study medication (14-AA-0042), the inpatient setting and other human laboratory studies performed in our Clinical Program at NIAAA, we anticipate that

approximately 25% of the enrolled participants may not complete the study. Therefore, we anticipate to enroll up to 55 subjects in order to reach at least 41 completers to satisfy the primary aim

I. Human subjects' protection plan

1. Consent documents and process

Procedures conducted before obtaining consent for this protocol

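### fMRI group maps: the cluster extent is pre-stated at 5 voxels, while the voxel threshold, cluster alpha and search volume that should determine it are not given, and the described group step does not test the drug

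*Combined protocol and SAP*

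**What the plan says.** Everything below is in Section H.1 (Analysis of data/ study outcomes) unless another section is named.

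- **Status of the outcome.** The Précis makes the drug effect on BOLD response to alcohol cues the main secondary aim. Section D lists it as secondary aim a, over three cue types (alcohol, food, sexual). The fMRI part of Section E names a picture set for control cues and calls the sexual cues exploratory.
- **General test.** Repeated-measures ANCOVA with drug condition as the within-subject factor is set for the primary outcome. Then: "Similarly, for secondary outcome measures, repeated measured ANCOVA will also be used". The level is general: "A probability level of 0.05 or lower will be considered significant".
- **Regression step.** A voxel counts as active on an F ratio at P = 0.05, "per voxel, uncorrected for multiple comparisons".
- **Contrast.** "We will also perform a subtraction analyses between different BOLD responses". Neither the drug conditions nor the cues are named here.
- **Group maps.** "To create the average activation maps, we will perform a random effect approach". The parenthesis that follows explains that amplitudes and t "values will be averaged in each voxel in standardized space across subjects".
- **Thresholding.** The group maps go through 3dClustSim, and "A cluster size of at least 5 voxels will be determined by Monte Carlo simulation".

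H.1 gives no voxel p for the group maps, no cluster-level alpha tied to them, no mask or region of interest (ROI) and no smoothness. The fMRI part of Section E supplies none of these. Section H.2 gives n = 27 for imaging.

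**The concern.** 3dClustSim takes a voxel threshold, a search volume, a smoothness and a target family-wise error, and returns the cluster extent. H.1 writes down an extent and leaves those inputs open. A reader who wants a complete thresholding rule can only pair the two numbers in the paragraph, P = 0.05 per voxel and 5 voxels. Over a large search volume in smooth data, that pair gives almost no protection against false clusters.

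The drug comparison is also loosely tied to the maps. Averaging amplitudes and t-values shows where the cues activate the brain. It does not ask whether drug and placebo differ relative to the variation of that difference between participants.

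At stake is whether a reported BOLD effect could be interpreted. This is not the primary outcome, but Section D says the primary and secondary outcomes together will guide whether a Phase 3 trial is run.

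**Working it through.** **1. Can the 5 voxels be reproduced?** No. That would need the group voxel p, cluster-level alpha, mask or voxel count, smoothness, sidedness and neighbour rule. None is stated for the maps, so only a range under assumptions can be shown.

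**2. Method.** Simulate Gaussian null maps. Keep voxels with |z| above the two-sided cut-off for p (1.96 at p = 0.05, 3.29 at p = 0.001). Join face-adjacent voxels of the same sign, and let M be the largest cluster. Then:

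- family-wise error of extent k: FWE(k) = P(M ≥ k)
- needed extent: the smallest k with FWE(k) ≤ 0.05.

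Assumed whole-brain mask: a 1.4 L ellipsoid. With 3 mm voxels it has 51,843 voxels (× 27 mm³ = 1.40 L); with 3.75 mm voxels, 26,513 (× 52.73 mm³ = 1.40 L). There were 1,000 maps per setting. At p = 0.05 about 51,843 × 0.05 = 2,592 or 26,513 × 0.05 = 1,326 voxels pass by chance. Smoothness decides how they clump.

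**3. Whole brain.**

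| Quantity | Voxel | FWHM 0 | 4 mm | 6 mm | 8 mm |
|---|---|---|---|---|---|
| P(any cluster ≥ 5), p = 0.05 | 3 mm | 0.303 | 1.000 | 1.000 | 1.000 |
| | 3.75 mm | 0.190 | 0.953 | 1.000 | 1.000 |
| Needed extent, p = 0.05 | 3 mm | 7 | 20 | 75 | 155 |
| | 3.75 mm | 6 | 9 | 33 | 79 |
| Needed extent, p = 0.001 | 3 mm | 3 | 4 | 10 | 19 |
| | 3.75 mm | 2 | 3 | 6 | 10 |

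At p = 0.05, 5 voxels is too few in all 8 settings. At p = 0.001 it is enough in 4 of 8 (needed extents 3, 4, 2, 3) and too few in the other 4 (10, 19, 6, 10).

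**4. Small regions.** Assumed spheres of 6, 8 and 10 mm radius (19-171 voxels), same voxel sizes and smoothness, p = 0.05, 4,000 maps each: P(any cluster ≥ 5) ran from 0 to 0.485. The needed extent was 2-4 voxels in 11 of 24 settings, where 5 is stricter than necessary, and 5-23 in the other 13.

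**5. Cross-checks.**

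- Null paired t-maps with n = 27 (df 26), p = 0.05, 100 maps per setting: 0.37, 1.00, 1.00, 1.00 at 3 mm and 0.17, 0.93, 1.00, 1.00 at 3.75 mm.
- A cubic mask of 36³ = 46,656 voxels, 200 maps: 0.26 unsmoothed, and 1.00 at FWHM of 1.5, 2 and 3 voxels. At 2 voxels (6 mm with 3 mm voxels) the needed extent was 70 at p = 0.05 and 10 at p = 0.001, against 75 and 10 in the table.

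**6. What the described group step estimates.** For participant i, let a(i, drug) and a(i, placebo) be the alcohol-minus-control amplitudes in the two stages. An average map estimates the mean of such amplitudes. The aim concerns d(i) = a(i, drug) − a(i, placebo), tested by t = mean(d) / (SD(d)/√n), with n − 1 = 26 degrees of freedom at n = 27. SD(d) is the between-participant variation of the drug effect. Averaging amplitudes, or averaging individual t-values, does not produce this statistic.

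**The case against.** The strongest reply is that H.1 leaves the cluster size to Monte Carlo simulation, so 5 reads most naturally as a floor. That is a fair reading. If the simulated extent governs, a floor cannot raise the error rate; at most it is conservative in a small ROI.

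The high error rates also join figures the plan does not join. P = 0.05 is attached to the regression step, a whole-brain search is nowhere stated, and the listed preprocessing (motion correction and realignment) mentions no smoothing. This stands, and it makes those rates conditional. Unsmoothed, the needed extent of 6-7 is close to 5, although an error of 0.19-0.30 is still well above 0.05. At p = 0.001, or in small ROIs, 5 can be adequate.

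On the drug test, the ANCOVA with drug condition as factor is carried over to secondary outcomes, and Section D defines this outcome as drug against placebo. The group step is also called a random-effects approach, which the parenthesis may only summarise. The Précis and Section E make alcohol the main cue and name the control pictures. So a drug-placebo comparison on alcohol cues is implied.

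Finally, this is a proof-of-concept study, imaging is optional, and Section D speaks of guidance and sets no decision rule.

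None of this supplies the missing inputs. On every reading the group voxel p and the search volume are unstated, and the general 0.05 level is not tied to the clusters. These could therefore still be chosen after the maps are seen.

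**Conclusion.** The point holds as a specification fault in the main secondary outcome and should be fixed. It does not touch the primary outcome. The plan names a suitable correction, pre-states its output and omits its inputs. Used literally at p = 0.05 over a whole brain, 5 voxels would give at least one false cluster with probability about 0.2-0.3 unsmoothed and 0.95-1.00 at 4-8 mm FWHM. These figures rest on an assumed 1.4 L mask, 3 or 3.75 mm voxels and Gaussian noise. They show a range and are not the trial's actual error rate.

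A reader might infer three stronger things that the documents do not support:

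- **That the plan has no multiplicity correction, or is bound to report false clusters.** 3dClustSim is named, and 5 may be only a floor.
- **That 5 voxels is wrong at any threshold.** It suffices in 4 of the 8 whole-brain settings at p = 0.001 and is stricter than needed in 11 of the 24 ROI settings at p = 0.05.
- **That no drug-placebo test is planned.** The ANCOVA sentence implies one. What is missing is its link to the maps: whether it runs per voxel or on an ROI summary, and how it feeds the cluster step.

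**What to change.** Revise the neuroimaging paragraph of H.1 before unblinding:

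1. For each participant and stage, estimate the alcohol-minus-control amplitude. Test the paired drug-minus-placebo difference against between-participant variance in a group random-effects or mixed model. State that this is how the secondary-outcome ANCOVA and the subtraction analysis apply to the imaging data.
2. Fix the mask or named ROIs, a strict group voxel threshold (for example p < 0.001, two-sided) and a cluster-level family-wise alpha of 0.05.
3. Let 3dClustSim return the extent from measured smoothness, in place of the pre-stated 5 voxels.
4. State that the uncorrected P = 0.05 rule applies to single-subject maps only.

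The cost is wording and routine AFNI settings, with no new data. The price is lower sensitivity to small or diffuse effects. Under the whole-brain assumptions above, p < 0.001 would need about 3-19 voxels at 4-8 mm FWHM. A pre-specified ROI test keeps more sensitivity but gives up the whole-brain search.

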The capacity for self-reflection or *reflective functioning* promotes insight. Schechter and colleagues (2006) have used video feedback to improve reflective functioning and insight in traumatized mothers with respect to their relationship with their young children. This improvement predicts a shift in mothers' attitudes toward their children that are more age-appropriate and less distorted by their own needs. In alcoholic patients, the greater the patient's capacity for reflective functioning, the greater the likelihood that intervention will alter the patient's intrinsic understanding of their alcoholism and therefore improve their insight and motivation. In addition to maintaining motivation over time, it is important to help recovering alcoholics gain the confidence that they are able to change their behavior. To this end, we will use feed forward self-modeling to help a patient construct an image of success beyond his or her current capacity for achievement. The self-modeling technique combines previously learned behaviors that are components of a new skill, to help an individual perform a new behavior (Dowrick, 2012).

D. Study Objectives:

The present protocol represents the UH3 (Phase 2a) of [name] NCATS grant.

We propose to test PF-05190457, a GHSR1a inverse agonist, as a novel treatment for AUD. This will be a Phase 2a, proof-of-concept (early-signal) human laboratory study with PF-05190457 (100mg b.i.d.).

Primary outcome measures:

The primary aim will be to determine whether PF-05190457 reduces alcohol cue-elicited craving assessed in a "bar-like" laboratory. This outcome will be assessed during the inpatient phase of the protocol.

Secondary outcome measures:

The two secondary aims will be to determine:

- a. Whether PF-05190457, compared to placebo, reduces brain BOLD response during exposure to alcohol, food and sexually appetitive cues, during a task-based fMRI scan

- b. Whether PF-05190457, compared to placebo, reduces food choices in a “virtual buffet” conducted in a virtual reality context.

These outcomes will be assessed during the inpatient phase of the protocol.

Tertiary outcome measures:

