The tertiary aim will be to determine whether Motivational Interviewing with Video Feedback (MIVF), compared to standard supportive counselling, will enhance motivation for abstinence in the outpatient setting as well as will increase time to first relapse and reduce alcohol drinking. This outcome will be assessed during the outpatient phase of the protocol. The primary and secondary outcomes of this study will provide guidance on whether a next large randomized controlled Phase 3 trial with PF-05190457 in AUD should be conducted. If that will be the case, the tertiary outcome will provide valuable information on which behavioral intervention may be combined to the pharmacological treatment with PF-05190457 in the future Phase 3 trial. Additionally, this tertiary outcome may provide beneficial information for studies conducted with other medications.

E. Study design and methods.

This

Overview. This Phase 2a human laboratory study is aimed to test PF-05190457 100mg b.i.d. for an early-signal of efficacy in treating alcoholism.

Design. A within-subject, counterbalanced, double-blind, placebo-controlled study using PF-05190457, in treatment- and nontreatment seeking individuals with AUD.

Screening. The screening process for this protocol is conducted under the 14-AA-0181 NIAAA screening protocol procedures conducted in the Outpatient Clinic and/or the Inpatient Unit. As routinely done at the NIAAA Intramural Clinical Program, the screening procedures and data collected in the 14-AA-0181 protocol will allow the Investigators to assess the eligibility criteria for this protocol. If suitable, subjects will be offered to participate in this protocol. If subjects agree and sign the consent form, they will be enrolled in the study and start the study procedures.

Study Procedures

This study includes an inpatient phase followed-up by an optional outpatient phase

INPATIENT PHASE

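### The 41 completers give 80% power only for a one-sided test; the ANCOVA F-test planned at 0.05 has about 70%

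*Combined protocol and SAP*

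**What the plan says.** The design compares drug with placebo in the same people (Section E, Design): "A within-subject, counterbalanced, double-blind, placebo-controlled study". Section D words the primary aim directionally: "The primary aim will be to determine whether PF-05190457 reduces alcohol cue-elicited craving".

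Section H.1 names the analysis: "repeated measures analysis of covariance (ANCOVA) will be used to analyze the primary outcome, with drug condition as the within-subjects factor". It sets the threshold in one sentence: "A probability level of 0.05 or lower will be considered significant". Neither sentence mentions direction.

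Section H.2 gives the inputs to the sample size. The effect is introduced with "We chose an effect size $d_z = 0.4$ which is consistent with effect sizes of cue reactivity", the error rate is given as "α err prob = .05" without sidedness, and the conclusion is "err prob) = .80, a sample size of 41 subjects will be needed". Section H.3 then allows for about 25% non-completion and sets accrual at 55 "in order to reach at least 41 completers to satisfy the primary aim".

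**The concern.** With two conditions per person, the drug effect in a repeated measures ANCOVA is tested by an F-test on one numerator degree of freedom. That test is equivalent to a two-sided t-test. A paired design with an effect of 0.4, two-sided alpha of 0.05 and 80% power needs clearly more than 41 people, so the sample size appears to have been worked out for a different test from the one in H.1.

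Two things are at stake. First, this is the study's only power calculation, since the fMRI sample size is taken from an earlier study of similar size. If the stated 80% does not belong to the planned test, a non-significant primary result is weaker evidence against the drug than H.2 implies. Section D says the primary and secondary outcomes will guide whether a Phase 3 trial is run. Second, with sidedness unstated, a result in the favourable direction with a two-sided p between 0.05 and 0.10 could be called significant or not, depending on a choice made after the data are seen.

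**Working it through.** **Inputs.** From H.2: dz = 0.4, alpha = 0.05, target power = 0.80, stated n = 41. From H.1: two-level within-subject drug factor, significance at 0.05 or lower. From H.3: 25% loss, 55 enrolled. Section M plans no interim or futility analysis, so no alpha is spent early.

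**Formula.** For n pairs, the paired t statistic follows a noncentral t distribution with n − 1 degrees of freedom and noncentrality dz × √n. Power is the probability that it passes the critical value, in one tail or in both.

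**Reproducing the plan's figure, one-sided 0.05.**
- n = 40: noncentrality 0.4 × √40 = 2.530, critical value 1.685, power 0.7997, just short of 0.80.
- n = 41: noncentrality 0.4 × √41 = 2.561, critical value 1.684, power 0.809.

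The smallest n is therefore 41, exactly the stated figure. A two-sided alpha of 0.10 also gives 41.

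**The same inputs, two-sided 0.05.**
- n = 41: noncentrality 2.561, critical value 2.021, power 0.705.
- n = 51: noncentrality 2.857, critical value 2.009, power 0.7999.
- n = 52: noncentrality 2.884, critical value 2.008, power 0.808.

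The smallest n is 52, which is 11 more completers than stated. The normal approximation, ((1.960 + 0.842)/0.4)² = 49.1, rounds up to 50, so a cruder formula does not explain 41 either.

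**Cross-check with the F-test.** The noncentrality is n × dz² = 41 × 0.16 = 6.56 on (1, 40) degrees of freedom. Power is 0.705, the same as the two-sided t. Giving up one more degree of freedom for a period or covariate term leaves it at 0.705.

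**Consequences.**
- False-negative risk at dz = 0.4: 1 − 0.705 = 0.295, against 0.20 stated.
- Effect detectable with 80% two-sided power at n = 41: dz = 0.448, and 0.448/0.4 = 1.12, so 12% larger than planned.
- Accrual: 41/0.75 = 54.7, which rounds up to the stated 55, so the allowance for loss is correct for 41. For 52 completers it would be 52/0.75 = 69.3, or 70 enrolled.
- If all 55 enrolled completed, two-sided power would be 0.83. At the planned loss there is no such cushion (55 × 0.75 = 41.25).

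**How the team tested this outcome before.** Section C (Figure 5) reports the pilot effect on cue-elicited craving as F(1,13) = 4.45 with p = 0.05. The ordinary F-test p-value is 0.055 and the one-sided value would be 0.027. The reported figure is the non-directional one.

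**The case against.** The best defence is that a one-sided test was meant. The aim asks only whether the drug reduces craving, a one-degree-of-freedom contrast can be tested directionally, and 41 is then exactly right. The protocol never uses the words one-sided, two-sided or F-test for the planned primary analysis, so the two-sided reading is also an inference. This stands as far as it goes: if a one-sided 0.05 test was intended, the sample size is correct and the omission is in H.1. But a directional aim is not a directional test. The model named in H.1 yields a non-directional F-test unless something else is declared, and nothing is.

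A second point is that the analysis is an ANCOVA, and covariates could recover power. Taking 0.4 as the unadjusted effect and using 39 degrees of freedom, a covariate that removes 10% of the residual variance lifts two-sided power at 41 to about 0.75. It takes about 20%, a correlation of about 0.45 with the paired difference, to reach roughly 0.80. Those percentages are assumptions. H.1 names no covariate and H.2 claims no gain, so this does not support the stated 80%, but it does mean the 70% should be described as unadjusted.

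Third, the study is a proof of concept, no document makes a null result a formal stop, and the pilot estimate of dz was 0.78, at which 41 completers give more than 0.99 power two-sided. All true. However, the protocol itself calls the pilot results very preliminary, and it chose 0.4 as its planning effect. The power claim has to be judged at that value. How readers would treat a null result is a matter of judgement; the arithmetic does not depend on it.

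**Conclusion.** The point holds. The 80% in H.2 belongs to a one-sided test at 0.05. The test described in H.1, read in the ordinary way, has power of 0.705 at the design effect, a shortfall of about 10 percentage points, and would need 52 completers for 80%. The allowance for loss and the accrual of 55 are correct for 41 completers.

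The conclusion rests on three assumptions: that dz = 0.4 is the standardised paired difference and already includes the within-person correlation, as the symbol implies; that the drug factor is tested by its standard F-test; and that no covariate gain is counted. If the sponsor meant a one-sided test, the sample size stands, but the plan must still say so. Under either reading the text has to change, because H.1 and H.2 do not describe the same test.

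**What to change.** Choose one of two corrections, before the primary result is known.

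- **Two-sided test kept.** Replace the conclusion in H.2 with wording such as: *With 41 completers and a two-sided alpha of 0.05, power is about 70% for dz = 0.4 and 80% for dz = 0.45, before any covariate adjustment.* State in H.1 that the test is two-sided.
- **One-sided test intended.** State in H.1 that the primary outcome is tested one-sided at 0.05 in the direction of reduced craving, and add the same sidedness to the alpha in H.2.

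The cost is one or two sentences. Both options keep 41 completers and 55 enrolled. The first makes the stated power less favourable; the second makes the evidential standard explicit. The figures of 52 completers and 70 enrolled show the size of the gap and are not a request to enlarge the study.

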Adults who fulfill the qualification criteria will be included, regardless of race, ethnicity, sex, or religious affiliation. At this stage of development of this compound (PF-05190457), the manufacturer recommends to exclude women of childbearing potential because reproductive and developmental toxicity studies with PF-05190457 have not been conducted. Therefore, in order to be eligible for this study, female participants must be menopausal or surgically sterile. Definition of menopause and requirements to proof menopausal status are detailed in the inclusion criteria section of the protocol. Proof (medical records, certification from an MD) of surgical sterility will be required. Furthermore, as the effects of this drug on fetal development are unknown, male subjects will be informed verbally and in the consent form that they must be abstinent or use specific precautions, which are detailed in the inclusion criteria section of the protocol, starting with the first dose of study drug and continuing for 28 days after their last dose of study drug.

4. Recruitment

Participants will be recruited through referrals from the NIH Volunteer Office, and from the Patient Recruitment and Public Liaison (PRPL) Office as well as through ResearchMatch.org (facilitated through PRPL). ResearchMatch is a voluntary service that matches people interested in being research participants with researchers conducting a wide range of studies. ResearchMatch is currently used for other protocols in our Clinical Program at NIAAA, as well as for many other NIH protocols. ResearchMatch is a Clinical and Translational Science Awards (CTSA) initiative funded by the National Center for Advancing Translational Sciences (NCATS), part of the National Institutes of Health. Furthermore, participants will also be recruited by word of mouth and through local advertisements. Advertisement language will be used as flyers with tear off tabs, posted on the NIH campus, campuses of universities and colleges in the greater Washington DC area, as well as in billboards of public places and public transportation services in the greater Washington DC area. Advertisements will also be posted in electronic and printed local media, including newsletters, websites and local newspapers in the greater Washington DC area (for example, the 'Express'). Listserv ad will be used on craigslist.org, under the volunteers' section, as well as in NIH and other local email distribution lists, that are moderated, and following approval from the managers of these lists. 'ClinicalTrials.gov' may also represent a source of recruitment. Finally, participants will also be recruited via the NIAAA Screening Protocol 14-AA-0181), as these protocols serve as the screening protocols not only for this study but also for other protocols at the NIAAA Intramural Clinical Program.

5. Children

Children < 18 years of age will not be studied.

6. Vulnerable populations

Vulnerable populations will not be studied.

7. Evaluation of Risks/Discomforts and Benefits ratio

1. Anticipated Benefit

This study does not offer direct benefit to participants. However, the outpatient phase will provide participants with behavioral intervention and counselling, from which they might benefit. Additionally, contemporaneous with their enrollment in the present protocol, subjects are enrolled in 14-AA-0181 which provides standard treatment on the inpatient unit which the subjects may receive if desired.

Classification of risk

Overall risk and discomfort in this study is "more than minimal". The increase over minimal risk, discomfort is minor, and every precaution and protection to minimize any risks will be taken as described in a previous section. This level is justified,

because it will markedly facilitate medication development for AUD, and thus contribute to addressing major unmet medical needs. As such, the risk:benefit ratio of the proposed study is favorable.

2. Justification of sensitive procedures

This study employs the use of placebo to evaluate the effects of the study medication under investigation. This is the required standard set by the FDA for evaluation of drugs.

J. Protection of Participants' Privacy and Confidentiality

This protocol is covered by a Certificate of Confidentiality (CoC). Strict subject confidentiality will be maintained throughout the study. Confidentiality and information technology standards are in place at the NIAAA intramural program to protect electronic repositories of patient data as well as other clinical patient related material. It is reasonably expected that these safeguards will protect participants' medical and personal health information, ensuring their privacy.

Information obtained in the course of participating in this protocol will become part of the patient's NIH medical record. Third parties may request access to this information. However, access will not be granted without the explicit, written consent of the subjects. Samples and data will be stored using codes that we assign. Data will be kept in password protected computers. Samples will be kept in locked storage. Only study personnel will have access to the samples and data. Additional biological specimens obtained under this protocol will be stored in locked storage in coded form (protocol identifier plus randomization nr), in -80 °C freezers located in [name] at URI.

K. Study Agents/Interventions

Study Drug

Description of study medication side-effects is based on the previous studies conducted by Pfizer as well as our previous study 14-AA-0042.

The most common side effects noted in studies giving PF-05190457 to humans are: somnolence (sleepiness), headache and fatigue (tiredness) as well as decrease in serum glucose, and increased heart rate.

Less common side-effects are: abdominal discomfort, abdominal distention, abdominal pain, upset stomach, diarrhea, constipation, defecation urgency, gastrointestinal sounds abnormal, flatulence, gastroenteritis, upper respiratory tract infection, nasal congestion, nasopharyngitis, rhinorrhea, oral herpes, elevated transaminases, rhabdomyolysis, arthralgia, pain, pain in extremity, pain in jaw, swelling, hot flush, conjunctival hyperemia, acne cystic, face edema, hemoglobin decreased, dizziness, paraesthesia, hypoaesthesia, lethargy, dermatitis contact, photosensitivity reaction, hematoma, hemorrhage, abnormal eye exam, muscular weakness, musculoskeletal chest pain, depressive mood, euphoria, drowsiness, increased appetite, insomnia, irritability, difficulties to concentrate and sweating.

Most of the side-effects were mild and a few of them were moderate. There were no severe side-effects.

Our team in the CPN lab as well as the CC nursing staff are well familiar with PF-05190457, as we have already conducted and successfully and safely completed another study with this drug (14-AA-0042). Risks of medication will be minimized through careful and detailed screening of participants to minimize recruitment of those who might be at higher risk for adverse events, as well as careful and detailed monitoring of adverse events and participant well-being during the study. As detailed in the research strategy, a screening visit will be performed before enrolling any subject, under the NIAAA Screening Protocol 14-AA-0181. This screening visit will include a comprehensive clinical assessment, including physical exam, testing, psychiatric and medical history, blood and urine tests, and interviews aimed at assessing all

inclusionary/exclusionary criteria listed. For enrolled subjects, adverse medication effects will be systematically evaluated and recorded. *Ad hoc* clinical, laboratory and diagnostic assessments may be performed, should a participant present with specific symptoms, as the clinical situation may dictate. If adverse events are serious or intolerable, participants will be withdrawn from the study and given treatment and or referral as the situation dictates. Concomitant medications will be evaluated carefully before randomizing participants, as detailed in the exclusion criteria section above.

Blood draw and finger stick

The total amount of research blood to be drawn for this protocol will be approximately 434 cc which is within the NIH Clinical Center guidelines. Risks of blood draws and finger sticks include discomfort or possible bruising (hematoma) at the site of needle entry. For blood draws, there is also a small risk of fainting or infection at the site of the needle stick. Risks from blood draws and finger sticks are minimized by experienced medical personnel who will perform these procedures using sterile technique and following universal precautions.

EKG recording

Subjects may experience some discomfort when electrodes will be removed from the skin, which should resolve quickly.

Rating Scales, Questionnaires and other Behavioral Assessments

Participants are asked to complete rating scales and questionnaires (paper-and-pencil or computerized) as part of the study. Some individuals may feel emotional discomfort answering some of the items on rating scales. Such stress will be managed by the study team. If needed, participants have immediate access to licensed health care professionals.

Cue-Reactivity

Alcohol cue-reactivity experiments are performed on a regular basis at NIAAA. Increased craving and distress may appear during the CR procedure. Staff members will monitor the participant via closed circuit monitor/video cameras installed in the 'bar-like' room and the participant will always be able to communicate with staff members. Should clinically significant symptoms appear, participants will have immediate access to licensed health care professionals. Additionally, these risks are minimized by the inpatient design of this protocol. Of note, alcohol cue reactivity experiments are performed only during the cue reactivity procedure, and the study does not include any alcohol administration at any point.

fMRI

Anxiety about enclosed spaces: some individuals experience claustrophobia when placed inside the magnet bore of the scanner. Participants will be warned about this in advance and advised not to participate if they are prone to experiencing anxiety in enclosed places.

Loud noise of scanner: fMRI is a noisy process which could possibly damage a person's hearing. To prevent this we require participants to wear foam earplugs and/or headphones while inside the scanner.

“Virtual Buffet”

Previous studies conducted at the NHGRI Immersive Virtual Environment Test Unit (IVETU) located at the NIH Clinical Center show the safety of this experimental procedure. In the virtual environment encounters previously conducted at NHGRI, there were no incidences of serious cybersickness. Some individuals may experience mild symptoms of motion sickness (also called cybersickness in this context). These symptoms may include mild dizziness, headache, eyestrain, blurred vision, light sensitivity, and/or nausea. Such symptoms are rarely strong and we will discontinue the virtual session should participants report onset of these symptoms. We will continue the virtual session only if the participant desires, all symptoms have subsided, and a clinician approved the continuation of the experiment. Participants will be screened so as

to exclude individuals with conditions or history that would make them particularly susceptible to cybersickness. Furthermore, they will be instructed and reminded to report any symptoms during the encounter.

Motivational Interviewing with Video Feedback

Motivational interviewing video feedback may be tedious, embarrassing or may provoke anxiety or craving. Study clinicians will be with patient at all times and relaxation techniques will be used if patients experience symptoms.

f. Wearable Sensors

Bed Sleep Sensor: The bed motion sensor device is a low-power electromagnetic sensor, which uses radio waves for detection operating at similar frequency as Wi-Fi. The power of the device is 1 milliwatt, which is approximately 1000 times lower than the power emitted by a mobile phone, and does not pose any health risk for the participant.

Thermal Camera: The thermal camera does not pose any physical risks to the study participants. Some study participants may have some psychological concerns about the thermal image. To help address these concerns, we will point out to the participants several important points: The thermal image only measures the temperature at the surface of the skin. It does not see anything under the skin. Participants shall be shown a sample thermal image and can see that many of the facial features are not recognizable. For the iPad tablet that is mounted on the wall, the participants can also be shown their own live thermal image, so they will see what the image looks like and they will feel comfortable using the device.

Risk of compensation for tasks

Although we expect that this will be rare, it is possible that being compensated will cause an inpatient participant with alcohol dependence to desire to purchase alcohol to such an extent that they will leave the hospital against medical advice. In order to decrease the risk of this, AUD inpatients will not be paid in cash on the day of testing, but will receive payment after discharge using the RVS system through the NIH/CC.

Additional Considerations

The PI, [name], is also the holder for the currently active FDA IND # 119,365 (with cross-reference Pfizer IND # 110,476) obtained for the previous protocol that tested this medication (14-AA-0042).

L. Plan for reporting unanticipated problems and adverse events

Adverse events, protocol deviations, unanticipated problems (UP), Unanticipated Adverse Device Effects (UADEs), serious adverse events are defined as described in NIH HRPP Policy 801-Reporting Research Events. The NIH Principal Investigators (PIs)/designee and, as applicable, non-NIH Investigators must report events to the IRB via the Reportable Event Submission Form (REF) in NIH iRIS. All adverse events, deviations, and unanticipated problems will be summarized and reported at the time of Continuing Review in accordance with this policy.

M. Data Safety and Monitoring Plan

The DSMP is consistent with the NIH SOP 17.4. Specifically:

1. *Monitoring mechanism:* this study is monitored by the NIDA/NIAAA Addictions DSMB
2. *Frequency of the monitoring:* Initial DSMB review takes place before the study begins. Subsequent DSMB reviews take place after each 10 patients who have been exposed to study drug, unless otherwise recommended by the DSMB during the interim monitoring reviews
3. *Stop or change rules:* The following rules are followed:
 - 3a. Criteria for individual subject withdrawal:
 - A Serious Adverse Event (SAE) that is judged by the Investigators as being related to the study drug;
 - At the discretion of the PI and/or MAI and/or other health care provider involved in the study based on adverse event (AE) severity, or self-reported symptoms and/or observed changes in patient's well-being as reported by health care providers including clinically significant changes in vital signs, weight/BMI, blood/urine laboratory values, etc.
